12/19/2019	
 - Modified number of study arms from 15 to 16 and clarified intervention components - Clarified randomization scheme and follow-up for Stage 1 and 2 - Provided final version of patient materials available as part of provider-facing interventions 	
 - We are testing 14 different possible enhanced EHR alerts for providers in Stage 1, not 13 different possible alerts. We have also slightly modified the components included in the EHR tools for providers. We have included a new study schema accordingly. - We are clarifying how we are planning to randomize providers in Stage 2 - We have finalized the customizable patient instructions included in the SmartSet order set for providers 	1/7/2020
3/6/2020	
 - Updated to 206 providers based on newer baseline data - Clarified randomization scheme for providers in Stage 2 - Provided newer study schema to reflect these changes - Added in NCT number for the trial 	
 - We clarified the number of providers based on inclusion/exclusion criteria, to more accurately reflect expected recruitment targets. - We also refined the randomization plan for Stage 2. 	3/27/2020
9/7/2020	
 - Updated Manual of Procedures - Clarified expected sample size based on updated feasibility data 	
 - These changes were made to reflect typographical modifications requested by the NIA and to ensure alignment across different documents in procedures for the study. 	9/10/2020
9/29/2020	
 - Clarified that a telehealth visit is also considered an encounter - Confirmed final expected sample size 	
 - These changes were made to reflect discussions with statistician and DSMB members. 	10/1/2020
11/2/2020	
 - Revised statistical nomenclature and stages of analyses 	
 - These nomenclature changes were made to reflect refinements with statistician. 	11/3/2020
2/9/2022	
 - Include replication trial to be completed at MGB 	
 - These revisions were made to include the replication cluster-randomized trial at MGB in compliance with the NIH Single IRB Policy. 	2/11/2022
4/13/2022	
 - Include optional survey for Atrius providers to be completed at the end of the trial 	
 - This addition was made to measure implementation outcomes and obtain feedback about the interventions from a broad range of primary care providers at Atrius. 	5/12/2022
6/15/2022	
 - Include optional qualitative interview of Atrius providers after the end of the trial 	
 - This addition was made to obtain detailed feedback about how to improve the deprescribing interventions and scale the interventions further at Atrius. 	6/22/2022
6/28/2022	
 - Include clarification about data to be collected for outcome evaluation 	
 - This addition was made to clarify that Medicare Beneficiary Identifier is being collected in order to conduct the linkage with administrative claims. 	6/28/2022
6/30/2022	
 - Clarify where the claims data are being accessed from 	
 - This addition was made to clarify that the Medicare claims data are being accessed from the National Institute on Aging (NIA), the funder, who partners with Acumen to manage the MedRIC to provide specific linked data for NIA-sponsored studies. 	8/12/2022
8/22/2022	
 - Addition of supplemental analysis plan for MGB replication trial and clarify aspects of analytic plan - Revise provider survey and interview remuneration process 	
 - This supplemental analysis plan was added to clarify details of analytic plan and MGB replication trial specific to that trial. - This revision is to comply with Atrius provider remuneration requirements. 	

1. Background and Rationale

The prescribing of inappropriate medications for older adults is extremely common in the United States, ranging from 12% in community settings to 40% of those who are institutionalized.¹⁻³ Benzodiazepines, anticholinergics, and sedative hypnotics are among the most commonly prescribed in circumstances that are inconsistent with practice guidelines.^{3,4} While inappropriate prescribing increases the risk of adverse health consequences for all patients, older adults are particularly vulnerable.^{2,5-7} Physicians' lack of awareness of alternatives, ambiguous practice guidelines, and perceived pressure of patients or caregivers are among the reasons why these drugs are used more than might be optimal.²

Reducing inappropriate use of these drugs may be achieved through decision support tools for physicians that are embedded in electronic health record (EHR) systems. While EHR strategies are widely used to support the informational needs of providers, these tools have demonstrated only modest effectiveness at improving prescribing.⁸⁻¹³ The moderate effectiveness of current clinical decision support tools is thought to be largely due to what content they contain and the lack of provider-focused design principles being used to develop them.^{14,15} Prior approaches have also been criticized for the sheer volume of alerts, the lack of clinical significance of the tools, and the poor/delayed timing of the clinical decision support (i.e., after the prescribing decision). Accordingly, the effectiveness of these tools could be enhanced by leveraging recently-gained insights from behavioral economics and other related sciences. Their application to EHRs has been limited, and they have not been used to reduce the prescribing of potentially harmful medications to older adults.

2. Study Aims

The overall goal of the proposed research is to evaluate whether EHR-based tools, optimized using behavioral science principles, reduce inappropriate prescribing among older adults. Our overall hypothesis is that thoughtful incorporation of behavioral principles into

EHRs will reduce inappropriate prescribing and adverse drug events among older adults compared to usual care.

The objectives and endpoints for the adaptive and replication trials are summarized below.

OBJECTIVES	ENDPOINTS	JUSTIFICATION FOR ENDPOINTS
Primary		
To determine whether EHR-tools designed using behavioral science principles are more effective than at reducing inappropriate prescribing of high-risk medications in older adults than standard EHR tools or usual care.	Composite of 1) discontinuation of high-risk medications (benzodiazepines, sedative hypnotics, or anticholinergics [in secondary analyses]) or 2) ordering a gradual dose taper for one of these medications	These outcomes are rapidly measurable using EHR data alone and will provide evidence of provider behavior change.
Secondary		
To examine whether behavioral science-based EHR tools reduce cumulative prescribing of high-risk medications in older adults compared with usual care.	Quantity of high-risk medication prescribed, defined by number of milligram equivalents of high-risk medications prescribed to patients in follow-up	These outcomes capture the extent to which high-risk medications are cumulatively prescribed to patients by all Atrius providers over the follow-up period.
Tertiary/Exploratory		
To evaluate whether behavioral science-based EHR tools reduce the risk of clinically-significant adverse drug events, falls, fractures, hospitalizations, or emergency room visits compared with usual care.	Rates of adverse drug events, falls, fractures, hospitalizations, and emergency room visits in follow-up; quantity of high-risk medications dispensed to patients in follow-up period	These outcomes measure clinical outcomes that are consequences of these high-risk medications, measured in medical and pharmacy administrative claims data.

3. Study Design

3.1 Study site

The adaptive trial will be conducted in outpatient and acute care practices of Atrius Health, a large integrated delivery network in eastern and central Massachusetts. The replication trial will be conducted in outpatient primary care practices at Mass General Brigham (MGB), specifically Mass General Hospital. Atrius and MGB both have a fully functional EHR, EpicCare (www.epicsys.com), that supports computerized ordering of medications. Atrius is

comprised of 29 clinical and multi-specialty outpatient locations with 875 physicians. MGB is comprised of 150 outpatient practices with over 1,800 physicians.

3.2 Overall design

We propose an open-label adaptive 2 Stage cluster-randomized, NIH-defined Stage III pragmatic trial to evaluate whether EHR-based tools designed using behavioral principles reduce inappropriate prescribing and adverse outcomes among older adults at Atrius Health (See Study Schema in Section 3.3). After the successful completion of the adaptive trial, we will replicate the parallel group trial at Mass General Brigham, specifically within MGH primary care practices. We hypothesize that these tools will reduce prescribing of high-risk medications (primary outcome), cumulative prescribing of high-risk medications (secondary outcome), and clinically-significant adverse drug events like sedation and confusion (tertiary outcome) and cumulative utilization of high-risk medications (tertiary outcome) compared with usual care.

Because there are many ways in which the tools could be structured and delivered, we will use an adaptive trial design at Atrius Health that involves two Stages of evaluation to rapidly identify which of many possible tools are most promising for changing provider behavior. We will randomize primary care providers at MGH to one of the 2 most promising treatment arms identified in the adaptive randomized trial conducted at Atrius Health or usual care. Primary care providers will be the unit of randomization.

3.2.1 Stage 1 Design

In Stage 1 of the trial, we will randomize approximately 200 primary care providers at Atrius Health approximately equally to either usual care or active intervention. Of the half of providers randomized to active intervention, we will randomize them equally to one of 15 active intervention arms. Providers randomized to one of the 15 active intervention arms will receive an EHR tool to guide the care of their eligible patients. Providers randomized to usual care will receive no EHR tool, as is current clinical practice. Providers will be eligible for the trial if they prescribed a

benzodiazepine or sedative hypnotic to at least one older adult in the 180 days prior to randomization. We will randomize providers within strata based on their clinic size and baseline rates of high-risk medication prescribing.

Eligible patients of these providers will be who meet the following criteria: 1) older adults (aged 65 years or more) and 2) who have been prescribed at least 90 pills of benzodiazepine or sedative hypnotic in the last 180 days.

After 6 months (dictated by the average number of observed data points, i.e., at least 1 eligible patient for whom the EHR tools fired per physician), an interim analysis of Stage 1 participants will be performed to rank the 15 active intervention arms based on their observed effect size at reducing prescribing of high-risk medications. Up to 5 of the most promising active intervention arms based on their effect size will be tested in Stage 2. If more than 5 are promising, we will choose the top 5. If 1 to 5 arms are promising, we will choose those for testing in Stage 2. If none are promising, we will combine active interventions within the arms based on the most effective factors. After this interim analysis, the Stage 1 providers in the “winning” arms (i.e., the promising arms) will be randomly assigned to continue to receive their original treatment assignments or to usual care to test holdover/persistency effects. Similarly, the Stage 1 providers assigned to treatment arms determined to be statistically inferior will be randomly assigned in equal proportions to one of the winning arms or to usual care.

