3.2.2 Stage 2 Design

In Stage 2, we will randomize the primary care providers at Atrius Health who were assigned to usual care in Stage 1 in equal proportions to up to one of the 5 most promising treatment arms or to continue to receive usual care. We will also randomize any additional providers who prescribed at least one eligible anticholinergic to at least one older adult in the 180 days prior to randomization for secondary analyses. Providers randomized to one of the 5 selected treatment arms will receive an EHR tool to guide their care of eligible patients. As in Stage 1, we will randomize providers based on demographic characteristics, patient case-mix factors, and

baseline rates of high-risk medication prescribing. Patient eligibility will be identical to that used in Stage 1 except patients will also be included if they had been prescribed at least 90 pills of eligible anticholinergics in the last 180 days. Follow-up in Stage 2 will last at least 8 months, until enough data points have accrued.

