7.3 Statistical analyses

7.3.1 *Analysis of the primary endpoints*

7.3.1a Adaptive trial

The unit of analysis is at the patient-level. Therefore, for the primary outcome, we will use a generalized linear mixed model for binary outcomes to adjust for physician-level

clustering and multiple patient observations per physician. The study arms will be analyzed using a multivariable regression model, in which each of features of the EHR tools (“factors”) will be included as covariates in an overall regression model that compares the effect of receiving an enhanced EHR decision support tool compared with usual care. In specific, these factors will include: timing of EHR tool (open encounter=1, order entry=0), whether a follow-up alert is enabled as part of the tool (yes=1, no=0), cold state outreach is used (yes=1, no=0), simplification is used (yes=1, no=0), sign-off is used (yes=1, no=0), pre-commitment is used (yes=1, no=0) or if different risks of the high-risk medications are presented within the EHR tool (yes=1, no=0). In this way, we will also observe and report an overall effect of the enhanced EHR tool compared with usual care as well as the effect of individual features through their coefficients in the model. We will conduct this interim analysis once at the end of follow-up in Stage 1 to determine the arms with the most potential promise. In specific, the 15 active arms will be ranked based on their observed effect size at reducing prescribing of high-risk medications from the covariate coefficients from the models. At the end of follow-up in Stage 1, we will also use these regression models to explore whether any of the intervention arms (defined by factors) are inferior to usual care. We will repeat these analyses at the end of Stage 2 using all available data to determine whether any of the intervention factors (and secondarily, arms) were more effective than usual care at reducing prescribing of high-risk medications. In secondary analyses, we will include anticholinergics.

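### Stage 2 usual care mixes never-exposed providers with providers whose tool was withdrawn; the final model as listed does not separate them and gives no estimate of the holdover effect

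*Combined protocol and SAP*

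**What the plan says.** Section 3.2.1 will "randomize approximately 200 primary care providers at Atrius Health approximately equally to either usual care or active intervention", and within the active half "we will randomize them equally to one of 15 active intervention arms". After about 6 months the arms are ranked: "Up to 5 of the most promising active intervention arms based on their effect size will be tested in Stage 2".

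Three streams then feed Stage 2 usual care:
- Providers in winning arms "will be randomly assigned to continue to receive their original treatment assignments or to usual care to test holdover/persistency effects" (3.2.1). No ratio is given.
- Providers in arms judged statistically inferior "will be randomly assigned in equal proportions to one of the winning arms or to usual care" (3.2.1).
- Providers who "were assigned to usual care in Stage 1 in equal proportions" are re-randomised to a winning arm or stay in usual care (3.2.2).

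No washout is described. Section 3.2.1 has no rule for an arm that is neither winning nor inferior.

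Section 7.3.1a specifies a mixed model for the binary composite. Its covariates are seven current-tool features: timing, follow-up alert, cold state outreach, simplification, sign-off, pre-commitment and risk framing. They sit within an overall comparison of an enhanced tool with usual care. For the final analysis: "We will repeat these analyses at the end of Stage 2 using all available data to determine whether any of the intervention factors" beat usual care, with whole arms as a secondary question. The primary analysis is unadjusted. The secondary adjustments in 7.3.1a and 7.3.5 list patient, provider and practice characteristics, not prior exposure or stage. Section 7 does not mention holdover.

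**The concern.** The plan treats persistence as a live possibility, since it randomises some providers off their tool to test it. The final model has no term that tells a withdrawn provider from one who never had a tool. If some effect persists, the usual-care reference is no longer clean usual care, and the tool-versus-usual-care estimate, which is the question for the end of Stage 2, is biased. Providers moved from an inferior arm to a winning arm raise the same difficulty on the tool side, because only the new arm's features are described.

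The documents themselves make carry-over plausible. The primary outcome counts the absence of any order during follow-up (6.2), and patient eligibility looks back 180 days (4.1), about the length of Stage 1. A patient whose drug was stopped late in Stage 1 under a tool can still qualify for Stage 2 and count as a success for a provider now in usual care. No lasting change in the provider's behaviour is needed.

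Separately, the question for which 3.2.1 randomises withdrawal has no planned analysis.

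**Working it through.** The plan gives no figure for the make-up of Stage 2 usual care or for carry-over, so there is none to reproduce.

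**Inputs.** From 3.2.1 and 3.2.2: about 200 providers, half active, 15 active arms, up to 5 winners, Stage 1 usual care split equally over the winners plus usual care. From 7.2: baseline 5%, odds ratio 1.15, within-provider correlation 0.3, 20 patients per provider. Assumed: five winners, a 1:1 split of winning-arm providers, equal patients per provider and, where inferior arms contribute, that all ten non-winning arms are inferior.

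**Step 1: streams into Stage 2 usual care.**
- Providers per arm: 100/15 = 6.67. Winners: 5 × 6.67 = 33.3. Others: 10 × 6.67 = 66.7.
- Never exposed: 100/6 = 16.7.
- Ex-winning: 33.3/2 = 16.7.
- Ex-inferior: 0 if no arm is declared inferior; 66.7/6 = 11.1 if split equally over five arms plus usual care; 66.7/2 = 33.3 if half go to usual care.

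**Step 2: previously exposed share, s.** The pooled column adds the 100 Stage 1 usual-care providers to the denominator.

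| Ex-inferior | Previously exposed | Share of Stage 2 usual care | Share of pooled usual-care provider-periods |
|---|---|---|---|
| 0 | 16.7 | 16.7/33.3 = 50% | 16.7/133.3 = 12.5% |
| 11.1 | 27.8 | 27.8/44.4 = 62.5% | 27.8/144.4 = 19.2% |
| 33.3 | 50.0 | 50/66.7 = 75% | 50/166.7 = 30% |

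With 1 to 5 winners and all other arms inferior, the Stage 2 share stays between 50% and 75%. With one winner and no inferior arm it is only 3.3/53.3 = 6%.

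**Step 3: attenuation.** If a fraction c of the tool effect persists after withdrawal, observed/true risk difference = 1 − s × c. Take c = 0.5 (assumed).
- Pooled, only ex-winners carry over: 0.5 × 16.7/166.7 = 5.0% to 0.5 × 16.7/133.3 = 6.3%.
- Pooled, all withdrawn providers carry over: 0.5 × 12.5% = 6.3% to 0.5 × 30% = 15%.
- Stage 2 only, ex-winners: 0.5 × 16.7/66.7 = 12.5% to 0.5 × 16.7/33.3 = 25%.
- Stage 2 only, all withdrawn: 0.5 × 50% = 25% to 0.5 × 75% = 37.5%.

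This weights provider-periods equally. A mixed model with provider effects will weight them somewhat differently, so the figures indicate scale only.

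**Step 4: on the plan's effect scale.** An odds ratio of 1.15 from 5% gives 5.71%, a difference of 0.71 points. A 5-6% attenuation is about 0.04 points; 15% is about 0.11 points. At s = 19.2% and c = 0.5, usual care becomes 5.07% and the odds ratio reads 1.13. In a Stage 2 comparison with s = 62.5% it reads 1.10.

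**Step 5: can holdover be estimated?** Yes. A design matrix with current tool, prior exposure, winning-arm status and the tool-by-prior-exposure interaction has full rank. Precision is poor. The variance of a provider mean is 0.05 × 0.95 × (1 + 19 × 0.3)/20 = 0.0159. For 16.7 versus 16.7 providers, SE = √(0.0159 × 2/16.7) = 4.4 points, and the difference detectable with 80% power is 2.8 × 4.4 = about 12 points.

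**Step 6: direction.** Positive carry-over pulls the estimate toward null. A second mechanism needs no carry-over: patients reduced in Stage 1 may fail the 90-pill criterion in Stage 2, which changes who remains among exposed providers' patients. An illustrative Stage 2 calculation took 10% to 50% of patients as open to reduction, a usual-care rate of 5% and a tool rate of 5.71% or 10%. The ratio of the mixed contrast to the never-exposed contrast ran from 0.70 to 1.09, so the shift can go either way.

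**The case against.** The strongest reply is that the gap is one of specification. Section 7.3.1a lists covariates but does not state how withdrawn providers are coded or whether they enter the reference group, so the merging is inferred from that list. The schema figure in 3.3.1 was not available for this point and may show the groups separately. That stands as a limit on certainty. It does not close the gap, because a schema does not add a model term.

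Four stronger readings are tempting, and the documents do not support them:
- *Holdover is inestimable.* Winning-arm providers are randomised to continue or stop, and never-exposed usual care runs in parallel. The contrast exists; it is unspecified and imprecise.
- *Tool effects shrink by 25-38%.* That needs a Stage 2-only comparison in which every withdrawn provider carries over. The plan describes an analysis of both stages together, and ex-inferior providers may have no effect to retain, or one of opposite sign, since 7.3.1a frames inferiority against usual care.
- *The bias must be toward null.* This needs positive carry-over; inferior arms and lost eligibility can act the other way.
- *The wrong arms will go to replication.* A shared reference shifts all arms together and barely alters their ranking, and 3.2.3 takes the two most promising arms even if none beats usual care.

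It is also fair to say that simply making never-exposed usual care the reference would lean on Stage 1: 100/116.7 = 86% of its provider-periods. The stages differ in length (6 versus at least 8 months), and the outcome depends on length of follow-up, so a stage term is needed as well.

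**Conclusion.** The point holds in limited form. Stage 2 usual care is mixed by design, the listed terms cannot tell withdrawn from never-exposed providers, and the holdover question has no analysis. About 50% to 75% of Stage 2 usual care is previously exposed under five winners, a 1:1 split of winners and, above 50%, all other arms inferior.

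In the pooled analysis that the plan describes, the likely distortion of tool versus usual care is modest: about 5-6% to 15% at an assumed 50% persistence, and larger in any Stage 2-only comparison. The assumption that matters most is the persistence itself, for which the documents give no figure. Because the issue concerns the control group of the primary comparison, it should be settled before the final analysis.

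**What to change.** In 7.3.1a:
- Add a stage term and two provider-period indicators: previously exposed and now usual care; and switched from another arm. The reference then becomes never-exposed usual care.
- Pre-specify two contrasts: withdrawn versus never-exposed in Stage 2 (holdover), and continued versus withdrawn among winning-arm providers (the effect of keeping the tool on). Report holdover as exploratory, given the detectable difference of about 12 points.
- Add a sensitivity analysis limited in Stage 2 to providers who were in usual care in Stage 1.
- State in 3.2.1 the split ratio for winning-arm providers, what equal proportions means for inferior-arm providers, and what happens to arms that are neither.

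No new data are needed. The cost is precision. With 16.7 + 11.1 = 27.8 withdrawn providers and 83.3 + 16.7 + 55.6 = 155.6 providers on a tool, the Stage 2 standard error for tool versus usual care rises from √(0.0159 × (1/155.6 + 1/44.4)) = 2.1 points to √(0.0159 × (1/155.6 + 1/16.7)) = 3.2 points. Stage 1 data soften this in the pooled model.

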5.3 Measures to minimize bias: randomization and blinding

Providers will be randomized to treatment arms in equal proportions based on blocks. We will use provider-based cluster randomization to minimize the possibility of contamination in study interventions between practices and clinic staff. For the randomization, we will use stratified randomization based on clinic practice size and baseline rates of prescribing to reduce potential imbalances between the providers assigned to the treatment arms.

The providers will not be blinded to which arm they were assigned to, as blinding is the context of an intervention that is intended to motivate action will be infeasible. The study statistician, in partnership with data analysts at Atrius Health, will generate and implement the randomization scheme, with oversight by the Principal Investigators. Investigators will be blinded to the treatment arms during interim and final analyses.

6. Study Assessments and Procedures

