6.2 Outcomes

For both Stages, the primary outcome will be a binary composite measure of a reduction in inappropriate prescribing, evaluated using EHR data from Atrius Health. In specific, we will measure a composite of 1) discontinuation of high-risk medications (benzodiazepines, sedative hypnotics, or anticholinergics [included in secondary analyses]), defined by either: a) active discontinuation and no subsequent order or b) no order during follow-up or 2) ordering a gradual dose taper (for benzodiazepine or sedative hypnotics). If either of these actions is taken by the provider for a specific patient at any point in the follow-up window, we will classify the patient as having had a reduction in inappropriate prescribing. If the patient has multiple therapeutic classes of interest (e.g., benzodiazepines and sedative hypnotics), we will classify patients with a reduction for any class as a “reduction” for the composite measure. In secondary analyses, we will include anticholinergics. We will also stratify patients by their number of eligible therapeutic classes (i.e., one, two, or three classes) and analyze outcomes within these strata.

In Stage 2 and the replication trial, secondary outcomes include the quantity of high-risk medication prescribed, defined by number of milligram equivalents of high-risk medications prescribed to patients in the follow-up period to capture cumulative prescribing by all providers

at Atrius Health. As above, we will also stratify patients by their number of eligible therapeutic classes (i.e., one, two, or three classes) and analyze outcomes within these strata.

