For the secondary outcome of cumulative medication prescribing, will use an identity link function and normally distributed errors within the generalized linear models. For tertiary adverse clinical outcomes and resource utilization outcomes, we will use a log link function and binary distributed errors within the overall multivariable models. These models generate the estimated relative risks (RRs) with robust standard errors and are considered to be particularly appropriate when outcomes are common (e.g., incidences of $\geq 10\%$). For these outcomes from claims data, we will follow patients whose providers are randomized to the study from the time

of randomization until they are censored due to loss of continuous enrollment in their health plan or leaving Atrius Health. Due to the nature of the randomization, we do not anticipate any systematic differences in the amount of follow-up time per arm but will account for any imbalances using inverse probability censoring weights.

Because this is a randomized trial, our primary analyses are planned as unadjusted; however, if there are strong patient-level predictors of the outcomes not balanced by stratified randomization, we will adjust for these in the primary analyses. Given the nature of the data and how the outcomes are being measured, there should not be missing values. However, should there be sufficient missing data (e.g., >10%), we will use multiple imputation.³¹

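### If Stage 2 pools separately randomised provider groups without a term for the group, its secondary and tertiary comparisons can be biased against the tools

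*Combined protocol and SAP*

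**What the plan says.** Stage 1 sets the stage: "we will randomize approximately 200 primary care providers at Atrius Health approximately equally to either usual care or active intervention", and "Of the half of providers randomized to active intervention, we will randomize them equally to one of 15 active intervention arms" (section 3.2.1). Selection follows the Stage 1 results: "Up to 5 of the most promising active intervention arms based on their effect size will be tested in Stage 2".

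Providers then enter Stage 2 by separate routes:

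- Former usual-care providers are randomised "in equal proportions to up to one of the 5 most promising treatment arms or to continue to receive usual care" (section 3.2.2).
- Winning-arm providers "will be randomly assigned to continue to receive their original treatment assignments or to usual care to test holdover/persistency effects" (section 3.2.1). No ratio is given there. Section 5.3 has the general rule: "Providers will be randomized to treatment arms in equal proportions based on blocks".
- Inferior-arm providers are randomised in equal proportions to a winning arm or usual care (section 3.2.1).
- Added anticholinergic prescribers are also randomised (section 3.2.2). Their number and ratio are not stated.

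On outcomes, section 6.2 says: "In Stage 2 and the replication trial, secondary outcomes include the quantity of high-risk medication prescribed". It gives the tertiary outcomes the same time frame. On adjustment, section 7.3.2 says: "Because this is a randomized trial, our primary analyses are planned as unadjusted". Its exception covers only strong patient-level predictors that stratification left unbalanced. The covariates listed in sections 7.3.1 and 7.3.5 do not include Stage 1 assignment. Section 7.3.3 calls for intention-to-treat analysis of all randomised patients and does not separate source groups.

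**The concern.** Randomisation justifies an unadjusted comparison only among units that had the same chance of each arm. In Stage 2, read naturally, that holds within a source group but not across groups. Winning-arm providers can reach only their own tool or usual care, so they are over-represented in usual care.

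They are also a selected group. With about 6.7 providers per arm, part of what makes an arm win is a chance mix of providers who deprescribe more anyway. If that tendency persists into Stage 2, usual care is enriched with such providers. The tools then look worse than they are, even if exposure to a tool leaves no lasting effect. The cost is lost power and a raised chance of a false signal of harm.

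**Working it through.** The plan gives no figure for the Stage 2 source mix or for this bias, so there is none to reproduce. From section 7.2 I take the 5% baseline rate, the odds ratio of 1.15, 20 patients per provider, and within-provider correlations of 0.3 (adaptive trial) and 0.1 (replication trial, used here as a lower value).

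**Planned effect.** Odds 0.05/0.95 × 1.15 = 0.0605, so the rate is 0.0605/1.0605 = 5.71%, or +0.7 points.

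**Source mix.** Inputs: 100 usual-care and 100 active providers, 100/15 = 6.67 per active arm, K winners. The chance of usual care is 1/(K+1) for former usual-care and inferior-arm providers. It is assumed to be 1/2 for winners. Added anticholinergic prescribers are left out. At K = 5:

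| Source group | Usual care | Tools |
|---|---|---|
| Stage 1 usual care (100) | 16.7 | 83.3 |
| Winning arms (33.3) | 16.7 | 16.7 |
| Inferior arms (66.7) | 11.1 | 55.6 |
| Total | 44.4 | 155.6 |

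Ex-winners are 16.7/44.4 = 37.5% of usual care and 16.7/155.6 = 10.7% of tool providers. The same arithmetic gives 27.8% against 8.8% at K = 4, 18.2% against 6.9% at K = 3, 9.7% against 5.1% at K = 2, and 3.3% in both at K = 1.

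**From mix to bias, with no tool effect and no carry-over.** Let Δ be the expected excess of winning-arm providers over the provider average. Formerly active providers average zero overall, so inferior-arm providers average -Δ × 33.3/66.7 = -Δ/2. The naive tool-minus-usual-care difference at K = 5 is

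Δ(0.107 - 0.375) - (Δ/2)(0.357 - 0.250) ≈ -0.32Δ,

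multiplied by the share of the provider difference that persists.

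**Size of Δ on the 5% composite (illustration only).** The patient variance is 0.05 × 0.95 = 0.0475. The mean of the five largest of 15 standard normal values is about 1.03. With correlation on the observed scale:

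- ICC 0.3: true arm variance 0.3 × 0.0475/6.67 = 0.00214; observed arm SD √(0.0475 × (0.3 + 0.7/20)/6.67) = 0.0489; Δ = 1.03 × 0.00214/0.0489 = 0.045. The bias is about -1.4 points with full persistence and -0.7 with half.
- ICC 0.1: true arm variance 0.000712; observed arm SD √(0.0475 × (0.1 + 0.9/20)/6.67) = 0.0321; Δ = 0.023. The bias is about -0.7 points with full persistence and -0.4 with half.

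Simulation over the same range gives about -0.4 to -1.5 points, and a source-group term cuts this to under 0.1 point. If 0.3 is read as a latent-scale correlation, the simulated bias with full persistence is about -0.4.

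**Continuous Stage 2 outcome.** A second simulation used 10 patients per provider in Stage 1. At a 5% rate and ICC 0.3 the bias was -0.020 SD (correlation 0.5 between Stage 1 and Stage 2 provider effects) to -0.043 SD (correlation 1). In the latter case two-sided type I error was 7.2%. Ranking arms by the factor model of section 7.3.1a gave -0.036 SD and 6.2%. Over rates of 5% to 40%, ICC 0.1 to 0.3 and correlation 0.5 to 1, the bias was -0.008 to -0.061 SD and type I error 5.5% to 9.3%. With source group in the model, bias was about zero and type I error 4.6% to 5.7%.

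**When it vanishes.** The bias is nil with one winner, if winners also go to usual care with chance 1/6, or if Stage 2 outcomes are unrelated to Stage 1 performance. It also cancels if half of the inferior-arm providers go to usual care: the shares become 25% and 12.5% for winners, 50% and 25% for inferior arms, and Δ(0.125 - 0.25) - (Δ/2)(0.25 - 0.50) = 0.

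**The case against.** The strongest reply is that pooling is inferred. Section 3.2.2 defines Stage 2 around former usual-care providers. The re-randomisation of winners sits in section 3.2.1 with its own purpose, to test persistency. If ex-winners answer only that question, this bias does not arise. The intention-to-treat sentence stands under baseline descriptive analyses. This objection stands as far as it goes, but nothing in the plan restricts the Stage 2 comparisons, and inferior-arm providers are re-randomised with no such separate purpose.

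The 1:1 split is also inferred. The Atrius schema (section 3.3.1) was not visible in the text reviewed and may settle it.

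Other points reduce the size:

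- Stratifying on baseline prescribing should shrink provider differences, though it does not equalise the odds across groups.
- Patients must again meet the 90-pill criterion, so those deprescribed in Stage 1 may leave, which weakens persistence.
- For claims outcomes a Stage 2-only window is not certain. Section 7.3.2 follows patients from randomisation, and the schedule in section 3.8 marks adverse drug events in Stage 1 follow-up.
- The figures in points are for the primary composite, not for the outcomes at issue.

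A reader might infer that every Stage 2 comparison is confounded outright, or that the primary analysis is too. The documents support neither. The first depends on the inferred ratio and pooling. The end-of-trial primary analysis uses all available data with provider clustering, which largely absorbs the problem when provider differences persist.

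**Conclusion.** The concern holds conditionally and the plan should address it. It rests on four assumptions: at least two winning arms; about half of winners but 1/6 of the others going to usual care; all groups pooled; and provider differences that persist and relate to the outcome.

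Under these, the direction is against the tools. In the five-winner illustration the bias ranges from somewhat smaller than the planned +0.7 points to about twice it. For quantity prescribed or dispensed some bias is plausible, but its size depends on an unknown correlation with Stage 1 performance. For falls, fractures and hospitalisations it may be near zero. The point concerns the adaptive trial's secondary and tertiary outcomes, not the replication trial.

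**What to change.** In section 7.3.2, include Stage 2 randomisation source group as a fixed effect, or stratify by it, in every Stage 2-only comparison that pools groups. The levels are Stage 1 usual care, winning arm, inferior arm and added anticholinergic prescriber. Alternatively, restrict the efficacy contrast to former usual-care providers and report the ex-winner contrast separately as the persistency analysis. In either case, state the winning-arm ratio, make the inferior-arm ratio explicit, and say which groups enter each comparison.

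The covariate is already known for every provider. The precision cost can be approximated by treating provider means as equally precise. The information is 44.4 × 155.6/200 = 34.6 when pooled. Within groups it is 100 × 5/36 + 33.3 × 1/4 + 66.7 × 5/36 = 31.5, so the standard error rises by a factor of √(34.6/31.5) = 1.05. Restricting to former usual-care providers leaves 13.9, a factor of √(34.6/13.9) = 1.58.

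One further cost remains with adjustment. The ex-winner stratum compares tool continued with tool withdrawn, so carry-over could dilute the combined estimate; showing that stratum separately would make this visible.
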